**Definition of Maintenance Phase baseline in the context of HRQoL assessments:**

Maintenance Phase baseline for HRQoL assessments is defined as the last available assessment conducted prior to or on the date of randomization, occurring no more than 28 days prior to randomization. If no such assessment exists, Maintenance Phase baseline will be the last available assessment after randomization and prior to the first dose of Maintenance Phase treatment.

**Definition of Maintenance Phase baseline in the context of ECOG PS assessments:**

Maintenance Phase baseline for ECOG PS assessments is defined as the last available assessment conducted prior to or on the date of randomization, occurring no more than 14 days prior to randomization. If no such assessment exists, Maintenance Phase baseline will be the last available assessment conducted after randomization and on or prior to the Maintenance Phase treatment start date.

**Definition of duration:**

Duration will be calculated by the difference of start and stop date + 1, if not otherwise specified. For example, survival time (days) = date of death – date of randomization + 1.

The time since an event (e.g. time since first diagnosis) will be calculated as reference date minus date of event.

**Definition of Induction Phase Study Day:**

Induction Phase Study Day is defined relative to the date of first administration of induction chemotherapy. Induction Phase Study Day 1 corresponds to the day of first administration of induction chemotherapy and the day before is defined as Induction Phase Study Day -1 (i.e., no Induction Phase Study Day 0 is defined).

**Definition of Maintenance Phase Study Day:**

Maintenance Phase study day is defined relative to the date randomization into Maintenance Phase. Maintenance Phase study day 1 corresponds to the day of randomization and the day before is defined as Maintenance Phase Study day -1 (i.e., no Maintenance Phase study day 0 is defined).

**Definition of study treatment, in the context of subjects randomized to receive BSC-only:**

Subjects randomized to receive BSC-only will be included in the overall counts for the control treatment arm, unless otherwise stated. “Study treatment” for subjects randomized to receive BSC-only, is considered to begin on the date of the Week 1 Day 1 assessment visit and continue until the

date given on the “End of Assessment” eCRF page, the date given on the “Study Termination” eCRF page, start day of new anti-cancer drug therapy – 1 day, or date of death, whichever comes first.

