#### **Safety for Maintenance Phase (Safety-Maintenance) Analysis Set**

The Safety-Maintenance analysis set will include all subjects randomized to receive active study medication (avelumab or chemotherapy) who received at least one dose of active study medication during the Maintenance Phase and subjects randomized to the control arm who are deemed not eligible to further chemotherapy and are planned per Interactive Web Response System (IWRS) to receive best supportive care (BSC) only, with no additional active treatment.

Subjects will be classified according to the treatment assigned at randomization unless the incorrect treatment(s) was/were received throughout the dosing period, in which case subjects will be classified according to the first study treatment received. In the case a subject randomized to receive active study medication receives no active study medication, that subject will be excluded from the Safety-Maintenance Analysis Set.

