### 11.1 Disposition of Subjects and Discontinuations

Subject disposition summary will be created for the Induction Phase and the Maintenance Phase separately.

For the Induction Phase, the following will be summarized overall and by Induction Phase study treatment for all screened subjects:

- Number of subjects screened
- Number of subjects screen-failed or not treated during Induction Phase
- Number of subjects discontinued during the Induction Phase
- Number and percentage of subjects who completed the Induction Phase treatment
- Primary reasons for treatment discontinuation during the Induction Phase
- Number of subjects completed Induction Phase (overall only)
- Number of subjects completed Induction Phase but not randomized (overall only) and primary reason

Subjects who discontinue Induction Phase chemotherapy due to completion of regimen/randomization to the avelumab or BSC-Only arms will not have the reason presented in the table.

For the Maintenance Phase, the following will be summarized overall and by treatment arm (as randomized) for all randomized subjects:

- Number of subjects randomized
- Number and percentage of subjects randomized but not treated (among those randomized to chemotherapy or avelumab)
- Number and percentage of subjects randomized to the control arm who received BSC-Only
- Number and percentage of randomized subjects still on study treatment
- Number and percentage of randomized subjects who discontinued all study drugs
- Number and percentage of subjects who discontinued any one study treatment and primary reason by study drug, i.e. avelumab, oxaliplatin, 5-FU, capecitabine.
- Number and percentage of subjects who discontinued treatment but are still in follow-up

- Number and percentage of subjects who discontinued the study and primary reasons
- Number and percentage of subjects who re-initiated avelumab treatment
- Number and percentage of subjects who discontinued avelumab treatment after re-initiation and primary reasons
- Number and percentage of subjects in the following analysis sets:
  - Safety-Induction
  - FAS
  - PP
  - Safety-Maintenance
  - HRQoL
  - PD-L1+
- The number of subjects randomized by region and country
- Cross tabulation: subjects randomized (avelumab, oxaliplatin + 5-FU, oxaliplatin + capecitabine, or BSC-Only, Total) versus subjects treated (avelumab, oxaliplatin + 5-FU, oxaliplatin + capecitabine, BSC-Only, or Not Treated).

In addition, the following will be summarized:

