## 14 Treatment Compliance and Exposure

*Analysis sets: Safety-Induction Analysis Set, Safety-Maintenance Analysis Set*

All dosing calculations and summaries will be based on the administration of study medications from the corresponding eCRF pages.

All subjects enrolled in this trial will start with a 12-week chemotherapy Induction Phase during which subjects receive oxaliplatin and either 5-FU or capecitabine (according to the dosing schedule in Section 6.2.2 and Table 2 in the CTP).

Subjects who experience a CR, PR, SD, or Non-CR/ Non-PD at the end of Induction Phase will be randomized to the Maintenance Phase.

**Best Supportive Care (BSC):** Best supportive care is defined as: treatment administered with the intent to maximize quality of life without a specific antineoplastic regimen.

Maintenance Phase treatment arms are as follows:

- **Avelumab arm:** Subjects randomized to the avelumab arm will receive an IV infusion of avelumab at a dose of 10 mg/kg (over the duration of 1 hour) once every 2 weeks (one cycle).
- **Chemotherapy/BSC arm:** Following the completion of the Induction Phase, site investigators will determine whether subjects are eligible to receive further chemotherapy during the Maintenance Phase. Subjects randomized to the Chemotherapy/BSC-only arm will receive the following:
  - **Oxaliplatin + 5-FU:** If subjects are deemed eligible to receive further chemotherapy and received oxaliplatin + 5-FU in the Induction Phase, they will receive the same regimen as they received in the Induction Phase, e.g. Oxaliplatin at 85 mg/m^2 IV on Day 1 plus leucovorin 200 mg/m^2 IV on Day 1 followed by 5-FU at 2600 mg/m^2 IV continuous infusion over 24 hours on Day 1, once every 2 weeks. Please refer to the CTP for alternative dosage/administration schedules.

- **Oxaliplatin + Capecitabine arm:** If subjects are deemed eligible to receive further chemotherapy and received oxaliplatin + capecitabine in the Induction Phase, they will receive the same regimen as they received in the Induction Phase, i.e. oxaliplatin at 130 mg/ m^2 IV on Day 1 with capecitabine at 1000 mg/m^2, twice daily for 2 weeks followed by a 1-week rest period once every 3 weeks.
- **BSC-Only:** Subjects who are not deemed eligible to receive further chemotherapy will receive BSC alone with no active therapy.

Analysis of exposure will be based on the calculated actual dose levels:

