### Dose Reductions

Dose reduction will be calculated for the chemotherapy arm only in the Maintenance Phase. Per study protocol, there will be no dose reductions for the avelumab treatment arm. A dose reduction is defined as an actual non-zero cumulative dose < 90% of the planned cumulative dose for a given treatment cycle. For subjects receiving Capecitabine or 5-FU as a push followed by a drip, any skipped doses within the cycle will be counted as part of the planned cumulative dose for the cycle (i.e. will contribute to the denominator of the calculation). Dose reductions are counted on a per-cycle basis and do not consider whether previous doses were reduced. The number of subjects with at least one dose reduction as well as a categorical breakdown of dose reductions (1 / 2 / 3 / >=4) will be summarized for the chemotherapy/BSC arm.

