## 16.1 Adverse Events

Treatment-emergent adverse events (TEAEs) are those events with onset dates occurring during the on-treatment period or if the worsening of an event is during the on-treatment period. In this study, there are two on-treatment periods, one for Induction Phase and one for Maintenance Phase.

All analyses described will be based on TEAEs (started during the on-treatment period) if not otherwise specified. The AE listings will include all AEs (whether treatment-emergent or not). AEs outside the on-treatment period will be flagged in the listings.

- **Related Adverse Events:** adverse events with relationship to study treatment (as recorded on the AE eCRF page, Relationship with study treatment = Related) reported by the investigator and those of unknown relationship (i.e. no answer to the question “Relationship with study treatment”).
- **Serious Adverse Events (SAE):** serious adverse events (as recorded on the AE eCRF page, Serious Adverse Event = Yes).
- **Adverse Events Leading to Treatment Discontinuation:** adverse events leading to permanent discontinuation of study treatment (as recorded on the AE eCRF page, Action taken with study treatment = Drug withdrawn).
- **Adverse Events Leading to Death:** adverse event leading to death (as recorded on the AE eCRF page, Outcome = Fatal, as well as AEs of Grade 5).
- **Immune Related Adverse Events (irAEs):** immune related adverse events are identified via customized MedDRA PT queries and additionally classified by medical assessment according to case definition (two level approach). Details are included in [Appendix IV](#).
- **Infusion Related Reactions (IRRs):** IRRs are identified based on a list of MedDRA PTs. The detailed criteria of the timing relationship to infusion are specified in [Table 14](#) of Appendix IV.

Unless otherwise specified, AEs will be summarized by number and percentage of subjects with the AE in the category of interest as described above, by treatment group, primary System Organ Class (SOC) and Preferred Term (PT) and by decreasing frequency based on the avelumab treatment arm.

Each subject will be counted only once within each SOC or PT. If a subject experiences more than one AE within a SOC or PT for the same summary period, only the AE with the strongest relationship or the worst severity, as appropriate, will be included in the summaries of relationship and severity.

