### **16.2.3 Other Significant Adverse Events**

*Analysis sets: Safety-Maintenance Analysis Set*

The following tables will be created for Maintenance Phase treatment-emergent irAEs by treatment group. Separate summary tables will present potential irAEs (those identified solely by MedDRA preferred term) and medically assessed irAEs (which meet the criteria outlined in [Appendix IV](#)). For the potential irAE tables, both treatment arms will be presented with counts, as applicable. Only the counts for the avelumab arm will be displayed in the medically assessed irAE summary tables. “Cluster” is a compilation of PTs that are categorized by immune-related event of special interest.

- The overall summary of irAEs table will include the following categories:
  - All irAEs
  - irAEs leading to death, by Cluster and PT
  - irAEs, by Cluster and PT

- irAEs, Grade  $\geq 3$ , by Cluster and PT
- irAEs leading to permanent treatment discontinuation, by Cluster and PT
- irAEs by Cluster and PT and worst grade
- irAEs leading to death, by Cluster and PT
- irAEs by Cluster and PT
- irAEs, grade  $\geq 3$ , by Cluster and PT
- irAEs leading to permanent treatment discontinuation by Cluster and PT
- irAEs by Cluster and PT and worst grade

A listing of all potential and reviewed irAEs will be provided with the relevant information and a flag for irAEs with onset outside of the on-treatment period.

The frequency (number and percentage) of subjects with each of the following will be presented for treatment emergent IRRs, by treatment group:

- The overall summary of IRR table will include the following categories:
    - All IRRs
    - Related IRRs
    - Serious IRRs
    - Related serious IRRs
    - IRRs, Grade  $\geq 3$
    - Related IRRs, Grade  $\geq 3$
    - IRRs leading to permanent treatment discontinuation
    - Related IRRs leading to permanent treatment discontinuation
    - IRRs leading to death
    - Related IRRs leading to death
  - IRRs leading to death, by PT
  - Related IRRs leading to death, by PT
  - IRRs, by PT
  - IRRs, Grade  $\geq 3$ , by PT
  - Related IRRs, by PT
  - Related IRRs, Grade  $\geq 3$ , by PT
  - IRRs leading to permanent treatment discontinuation, by PT
-

- Related IRRs leading to permanent treatment discontinuation, by PT
- Serious IRRs, by PT
- Related serious IRRs, by PT
- Time related to first onset of an IRR (infusion 1, infusion 2, infusion 3, infusion 4 or later)

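### Control-arm percentages for infusion reactions and drug-withdrawal AEs include best-supportive-care-only subjects who get no study drug, so they should not stand alone as chemotherapy rates

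*SAP*

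**What the plan says.** **Who is in the control column.** SAP section 10 sets the Maintenance Phase columns as avelumab against chemotherapy and BSC combined, and in its definition of study treatment for BSC-only subjects adds: "Subjects randomized to receive BSC-only will be included in the overall counts for the control treatment arm, unless otherwise stated". Section 14 says of these subjects: "Subjects who are not deemed eligible to receive further chemotherapy will receive BSC alone with no active therapy".

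**Who is in the safety set.** Under SAP section 9, avelumab and chemotherapy subjects enter the Safety-Maintenance set only after at least one dose: "In the case a subject randomized to receive active study medication receives no active study medication, that subject will be excluded". The same set also takes "subjects randomized to the control arm who are deemed not eligible to further chemotherapy and are planned per Interactive Web Response System (IWRS" to receive BSC only, with no dosing condition.

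**Denominator.** Protocol section 8.5.1 bases proportions on the number of subjects in the analysis set unless the SAP specifies otherwise.

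**Events that depend on a drug.**
- IRRs: SAP section 16.2.3 says that numbers and percentages "will be presented for treatment emergent IRRs, by treatment group". Table 15 in Appendix IV requires onset on the day of a study drug infusion or, for the named reaction terms, also the day after.
- Discontinuation: SAP section 16.1 defines these AEs as "adverse events leading to permanent discontinuation of study treatment (as recorded on the AE eCRF page, Action taken with study treatment = Drug withdrawn". Section 16.1.2 tabulates them as number and percentage by treatment group.
- Drug administration: SAP section 14 gives numbers and percentages of subjects with dose delays and with interruptions, both for IV drugs. Protocol section 8.5.6 gives the number and percentage of non-compliant subjects on the Safety-Maintenance set. SAP section 14 also leaves BSC therapy out of the compliance and exposure calculation.
- Dose reductions: SAP section 14 first restricts the calculation to the chemotherapy arm, notes that avelumab has no dose reductions, then says that the counts "will be summarized for the chemotherapy/BSC arm".

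**A restricted denominator elsewhere.** SAP section 11.1 limits one disposition row: "Number and percentage of subjects randomized but not treated (among those randomized to chemotherapy or avelumab".

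**The concern.** For most adverse events a BSC-only subject can be a case, and pooling simply describes the control strategy. The tables at issue are different, because their event definitions presuppose a drug. A subject with no infusion cannot have an IRR under Table 15, and a subject with no study drug has nothing to be withdrawn. In these tables the avelumab denominator is wholly at risk and the control denominator is not.

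The consequence is one of interpretation. A reader will tend to take the control percentage as the rate of infusion reactions or drug withdrawal on continued chemotherapy. It is lower than that by an amount set by how many controls were assigned to BSC, which says nothing about the tolerability of either drug.

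**Working it through.** The plan states no figure for this point, so there is nothing to reproduce first. The check has two parts.

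**1. Tracing each output**

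| Output | Can a BSC-only subject be a case? | Percentage by arm? | Is the BSC-only subject in the control denominator? |
|---|---|---|---|
| IRRs (SAP 16.2.3, Table 15) | No | Yes | Yes, by default; no exception stated |
| AEs leading to discontinuation (SAP 16.1, 16.1.2) | No, as inferred from the definition | Yes | Yes, by default; no exception stated |
| Dose delays, interruptions (SAP 14) | No; IV drug only | Percentage stated; by group for delays | Unclear: BSC therapy is excluded from the calculation, but nothing is said about BSC-only subjects |
| Non-compliance (Protocol 8.5.6, 6.9) | No; needs missed administrations | Yes, on the Safety-Maintenance set | Same uncertainty |
| Dose reductions (SAP 14) | No; needs a non-zero dose below 90% of plan | No percentage named; no avelumab figure | The text names both the chemotherapy arm and the chemotherapy/BSC arm |

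**2. Size**

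Let p be the event rate among chemotherapy-dosed controls and f the BSC-only share of the control Safety-Maintenance set. BSC-only subjects contribute no cases, so:

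- reported control rate = p × (1 − f)
- avelumab-to-control ratio = (ratio with dosed controls) × 1/(1 − f)

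Inputs: 499 randomized (Protocol 5.1.1) at 1:1 (Protocol 6.3) gives 499/2, or about 249 controls, all assumed to be in the set. The documents do not give f; the range 5% to 30% is an assumption.

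| f | BSC-only of 249 | p = 10% reported as | p = 20% reported as | Ratio multiplied by |
|---|---|---|---|---|
| 5% | 12 | 9.5% | 19.0% | 1/0.95 = 1.05 |
| 10% | 25 | 9.0% | 18.0% | 1/0.90 = 1.11 |
| 20% | 50 | 8.0% | 16.0% | 1/0.80 = 1.25 |
| 30% | 75 | 7.0% | 14.0% | 1/0.70 = 1.43 |

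Example at f = 10%: 249 − 25 = 224 dosed; 0.20 × 224 = 44.8 cases; 44.8/249 = 18.0%. If the avelumab rate were also 20%, a ratio of 1.00 against dosed controls would appear as 20/18 = 1.11.

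**The case against.** The strongest reply is that the control strategy is chemotherapy or BSC. Protocol section 8.5.2 defines the comparator that way, and Protocol section 5.1.1 has the investigator choose between the two before randomization. For that strategy, a BSC-only subject with no infusion reaction is a true zero and the pooled percentage is correct. This stands. A reader might infer that the pooled tables are biased and that the control denominator should simply be replaced by dosed subjects. The documents do not support that. Because the choice precedes assignment, subjects who would have been given BSC are also in the avelumab arm; removing them from control alone would compare all dosed avelumab subjects with a selected control subset.

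The reply does not settle the matter, because the safety set is not purely as randomized: undosed active-drug subjects are dropped from it.

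Three further points stand in part:

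- SAP section 11.1 reports the number of BSC-only controls and cross-tabulates randomized against received treatment, so a reader could rescale approximately. The IRR rate per infused subject may still not be recoverable, since Protocol section 5.1.2.2.2 allows single-agent capecitabine, an oral drug.
- That withdrawal of drug cannot be recorded for a BSC-only subject is an inference. SAP section 10 gives these subjects a nominal study treatment period, and the eCRF options are not shown.
- Safety is descriptive only (Protocol 8.5.5, SAP 16). No test or decision rule uses these rates.

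**Conclusion.** The point holds for IRRs and, subject to the eCRF inference above, for AEs leading to discontinuation. As written, the control percentage is the chemotherapy-dosed rate multiplied by (1 − f), while every avelumab subject in the set is dosed. The direction is certain whenever f and the dosed rate are above zero: control looks better and avelumab relatively worse. The size cannot be fixed from the documents; the relative understatement equals f, so it runs from 5% to 30% over the assumed range.

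For dose delays, interruptions and non-compliance the same dilution applies unless the exclusion of BSC therapy is read as also removing BSC-only subjects. The text does not say, so the finding there is an unclear denominator.

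A reader might also infer that dose-reduction rates distort the comparison between arms. They cannot: the avelumab arm has none by design and the SAP names no percentage. The only defect there is that two different arm labels are used for one summary.

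Nothing here touches the efficacy analyses or type I error. It matters for how tolerability percentages are read, and it is cheap to correct before the tables are produced.

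**What to change.** 1. **SAP 16.1.2 and 16.2.3.** Keep the pooled chemotherapy/BSC column. Beside it, for IRRs and AEs leading to discontinuation, add chemotherapy-dosed and BSC-only sub-columns, with at least one infusion as the chemotherapy denominator for IRRs. Label the dosed-only control column as not a randomized contrast.
2. **Same sections, if the pre-randomization choice is recorded for both arms.** Add a table restricted in both arms to subjects pre-designated for chemotherapy. This is the version that compares like with like.
3. **SAP 14.** State that percentages for dose reductions, delays, interruptions and non-compliance use subjects who received at least one dose of the relevant Maintenance study drug, and use one arm label throughout the dose-reduction paragraph.

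Cost: SAP wording and a few extra table columns. BSC-only status for controls is already held in the IWRS, so no new data are needed for items 1 and 3. Pooled columns for all other AE tables are unchanged.

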**Definition of treatment day:**

Treatment day is defined relative to the start date of study treatment within a given Treatment Phase. Treatment Day 1 is defined as the first day study treatment within a given Phase; Treatment Day -1 is defined as the day prior to the start of the given treatment. Treatment Day 0 is not defined. For example, for the Induction Phase, Treatment Day 1 is defined as the first day of Induction Phase chemotherapy and the day before is defined as Treatment Day -1. Similarly, for subjects randomized to active treatment during Maintenance Phase, Treatment Day 1 is defined as the day the first dose of Maintenance Phase study drug was given. For subjects randomized to receive BSC-only during Maintenance Phase, Treatment Day 1 is defined as the date of the Week 1 Day 1 assessment visit.

